#### 3.4.2 UMSARS

UMSARS Part I total scores, Part II total scores, Part III and Part IV will be respectively summarized by treatment group over time using descriptive statistics. If any of the items is missing in Part I or Part II, then the corresponding total score is considered missing.

The MMRM analysis specified in 3.4.1 will be used to analyze the change in Part I total scores from baseline, and the change in Part II total scores from baseline, respectively.

#### 3.4.3 *MSA-QoL*

At each visit, life satisfaction and change from baseline will be summarized by treatment using descriptive statistics. The change in satisfaction from baseline will be analyzed by the MMRM specified in 3.4.1.

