9.4. Statistical Analyses

All statistical summaries will be descriptive in nature. All results will be presented separately for each of the study intervention groups. All analyses, summaries and listings will be performed using SAS version 9.4 or later.

All continuous variables will be summarized by presenting the number of participants, mean, standard deviation (SD), median, minimum and maximum. Categorical variables will be presented as frequencies and percentages.

A separate Statistical Analysis Plan (SAP) will be prepared to provide additional details on the definitions of the safety and efficacy variables, analysis approach, statistical justification

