# 2.3 Study Endpoints

#### 2.3.1 Efficacy Endpoints

Efficacy endpoints include the change from baseline to Weeks 4, 8 and 12 in the following parameters:

- Goniometric measurement for "lateral" and "anterior" displacement
- Unified MSA Rating Scale (UMSARS) Part II
- MSA Health-Related Quality of Life (MSA-QoL) scale

- Montreal Cognitive Assessment (MoCA) scale (Week 12 only)
- Unified Dystonia Rating Scale (UDRS)

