#### 2.3.1.1 Goniometric measurement

Goniometric measurement of "lateral" and "anterior" displacement is determined using a wall goniometer and expressing the value in degrees in the range of 0-90.

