#### 2.3.1.2 UMSARS

The Unified MSA Rating Scale (UMSARS) consists of four parts:

- Part I Historical Review has 12 questions rated from 0 to 4, giving a range of 0-48 in the total score. Higher values indicate worse functional situation.
- Part II Motor Examination Scale has 14 questions rated from 0 to 4, giving a range of 0-56 in the total score. Higher values indicate worse functional situation.
- Part III Autonomic Examination has assessments of systolic blood pressure, diastolic blood pressure, heart rate and orthostatic symptoms (yes/no). Blood pressure and heart rate are measured after 2 minutes of rest and again after 2 minutes of standing.
- Part IV Global Disability Scale ranges from 1 to 5 (1=completely independent; 2=not completely independent; 3=more dependent; 4=very dependent; 5=totally dependent and helpless).

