#### 2.3.1.3 MSA-QoL

The MSA Health-Related Quality of Life (MSA-QoL) scale has 40 questions on an ordinal scale of "no problem", "slight problem", "moderate problem", "marked problem", and "extreme problem". Additionally, patients were asked to indicate life satisfaction at the moment on a scale of 0 (extremely dissatisfied) to 100 (extremely satisfied).

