#### 2.3.1.4 MoCA

A score ranging from 0 to 30 will be recorded for each patient according to the Montreal Cognitive Assessment (MoCA) scale. Higher scores indicate better cognitive function.

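### The SAP defines no score for the 40-item MSA-QoL scale, a named efficacy endpoint; it models only the additional life-satisfaction rating and does not declare the change

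*SAP*

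**What the plan says.** The efficacy objective (Protocol 3, SAP 2.1) covers motor function and/or quality of life. Under it, the objectives table in Protocol 3, the endpoint list in Protocol 9.4.2 and SAP 2.3.1 all name change from baseline in the "MSA Health-Related Quality of Life (MSA-QoL) scale". Protocol 9.4.2 asks for the value and its change to be summarised at each visit, and for an ANCOVA with the baseline score as covariate.

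SAP 2.3.1.3 describes the instrument: "The MSA Health-Related Quality of Life (MSA-QoL) scale has 40 questions on an ordinal scale", with five verbal categories running from no problem to extreme problem. It then introduces a further, separate rating: "Additionally, patients were asked to indicate life satisfaction at the moment on a scale of 0 (extremely dissatisfied) to 100 (extremely satisfied".

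SAP 3.4.3, headed MSA-QoL, has two sentences. The first summarises life satisfaction and its change by treatment at each visit. The second specifies the model: "The change in satisfaction from baseline will be analyzed by the MMRM specified in 3.4.1". The 40 questions are not mentioned there.

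SAP 5 lists three kinds of change from the protocol: renamed populations, MMRM in place of ANCOVA for every efficacy endpoint except MoCA, and no shift tables. SAP version 1.0 reads the same on all these points, and the version history records only a dictionary update for version 2.0.

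**The concern.** The SAP's own description makes life satisfaction an addition to the 40 questions, yet it is the only variable analysed under the scale's name. A general rating of satisfaction with life says something about quality of life. It is not the health-related quality of life that the 40 questions measure.

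Two things are at stake. First, the trial would finish without a pre-specified result on the named scale, and a reader could take the life-satisfaction result for the MSA-QoL result. Second, any 40-item score built after unblinding would be post hoc: total or subscales, direction and the handling of missing items would all still be open choices.

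**Working it through.** No sample size, power or error rate is involved, so the main check sets the sections side by side.

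**1. What the SAP defines for each efficacy measure**

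| Measure | Score range stated | Missing-item rule | Model |
|---|---|---|---|
| Goniometry, lateral and anterior (2.3.1.1, 3.4.1) | 0-90 degrees | single measurements | MMRM |
| UMSARS Part I (2.3.1.2, 3.4.2) | 0-48 | any item missing: total missing | MMRM |
| UMSARS Part II (2.3.1.2, 3.4.2) | 0-56 | any item missing: total missing | MMRM |
| MoCA (2.3.1.4, 3.4.4) | 0-30 | none stated | ANCOVA |
| UDRS (2.3.1.5, 3.4.5) | 0-112 | any factor missing: total missing | MMRM |
| Life satisfaction (2.3.1.3, 3.4.3) | 0-100 | single item | MMRM |
| MSA-QoL, 40 questions (2.3.1.3) | none | none | none in 3.4.3 |

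The SAP's wording for the other measures shows the level of detail it normally gives: "expressing the value in degrees in the range of 0-90" for goniometry, "Part II Motor Examination Scale has 14 questions rated from 0 to 4, giving a range of 0-56 in the total score" for UMSARS, "A score ranging from 0 to 30 will be recorded for each patient" for MoCA.

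The stated ranges for the summed scales can be reproduced from their item counts:

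- UMSARS Part I: 12 × 4 = 48
- UMSARS Part II: 14 × 4 = 56
- UDRS: 14 × (4 + 4) = 112

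The same cannot be done for MSA-QoL, because the five categories have no numeric codes. For illustration only, coding 0-4 would give a sum of 0 to 40 × 4 = 160, and coding 1-5 would give 40 × 1 = 40 to 40 × 5 = 200. The documents do not choose between these, or say whether a sum is intended at all.

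**2. Whether another section fills the gap**

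- SAP 5 moves every efficacy endpoint except MoCA to MMRM. That changes the model and supplies no response variable for MSA-QoL.
- SAP 3.1.4 says categorical data are summarised by counts and percentages. No section applies this to the 40 questions, and item-level counts would not give a change-from-baseline endpoint.
- SAP 6 refers to separate programming specifications, which are not among the documents. Protocol 9.4 gives the task of definition to the SAP: "A separate Statistical Analysis Plan (SAP) will be prepared to provide additional details on the definitions of the safety and efficacy variables".

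**3. Size by count**

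The scale is scheduled at Baseline and Weeks 4, 8 and 12, so four times. Per completing patient:

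- responses collected: (40 + 1) × 4 = 164
- responses with no specified use: 40 × 4 = 160

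**4. Why a missing-item rule must be part of the definition**

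Suppose the UMSARS rule (any item missing makes the total missing) were carried over, and each item were independently missing with probability p. The chance of a complete score at one visit with k items is (1 − p)^k. The values of p are assumptions; the documents give none.

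| p | 14 items (UMSARS Part II) | 28 inputs (UDRS, 14 areas × 2) | 40 items (MSA-QoL) |
|---|---|---|---|
| 0.5% | 0.995^14 = 93% | 0.995^28 = 87% | 0.995^40 = 82% |
| 1% | 0.99^14 = 87% | 0.99^28 = 75% | 0.99^40 = 67% |
| 2% | 0.98^14 = 75% | 0.98^28 = 57% | 0.98^40 = 45% |

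If missing items cluster in the same patients, the loss is smaller than shown.

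**The case against.** The strongest reply is that the SAP has not dropped the scale. SAP 2.3.1 keeps it as an endpoint, SAP 3.1.5 says efficacy endpoints will be tested on means, SAP 5 assigns MMRM to all of them except MoCA, and the descriptive summaries in Protocol 9.4.2 are not withdrawn. On that reading 3.4.3 is merely incomplete, and nobody decided to replace the scale with life satisfaction. This is fair as far as intent goes: no sentence says that one replaces the other. It does not supply a score, though, and a general commitment to model an endpoint cannot be carried out when the variable is undefined. The effect is a substitution whether or not one was intended.

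Second, 3.4.3 openly calls its variable life satisfaction, so the outputs may be labelled correctly. That is possible, and it would reduce the risk of misreading. It would still leave the named endpoint without a result.

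Third, the missing-item table rests on assumed rates, on independence and on a rule the SAP does not apply to this scale. That stands. The table shows only that the rule needs to be chosen; the finding does not depend on it.

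Fourth, this is an exploratory pilot with safety as its primary objective, and the efficacy objective is worded as and/or. That also stands, and it limits how serious the point is.

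**Conclusion.** The concern holds. The SAP names the MSA-QoL scale as an efficacy endpoint, defines no score for its 40 questions, directs the only MSA-QoL analysis at the additional single rating, and does not declare this in SAP 5. In consequence 160 of 164 responses per completing patient have no specified use, and the quality-of-life part of the efficacy objective depends on one global item. These conclusions come from the text and the visit schedule alone. Only the percentages for complete scores rest on assumptions. The matter should be fixed, but it concerns a non-primary endpoint: neither the safety evaluation nor the UMSARS analysis changes. A score may exist in the separate programming specifications, which could not be seen. It would still belong in the SAP.

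**What to change.** Before unblinding, amend SAP 2.3.1.3 and 3.4.3 as follows:

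- Define the score or scores from the 40 questions according to the instrument's own scoring, which the documents do not reproduce: item codes, subscales and/or total, range and direction.
- State an explicit missing-item rule for this scale.
- Summarise value and change at Baseline and Weeks 4, 8 and 12, and analyse change with the MMRM in 3.4.1.
- Keep life satisfaction as an additional variable under its own label.

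If the sponsor does mean to drop the scale score, SAP 5 should say so with a reason, and the endpoint in SAP 2.3.1 should be renamed life satisfaction. If unblinding has already taken place, a 40-item score can still be reported, but it should be labelled post hoc. SAP 1 already requires deviations after database lock to be documented in the study report.

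The cost is SAP wording, one or a few derived scores and the matching model runs. The responses are already scheduled for collection, so no new data are needed.

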#### 3.4.4 MoCA

MoCA scores will be summarized by treatment group using descriptive statistics at the Screening visit and Week 12. Change from Screening at Week 12 will also be summarized using descriptive statistics, and analyzed by an analysis of covariance (ANCOVA) model including treatment group as a factor, and baseline score as a covariate. P-values will be reported.

#### 3.4.5 UDRS

At each visit, UDRS total scores and change from baseline will be summarized by treatment using descriptive statistics. The change in UDRS total score will be analyzed by the MMRM specified in 3.4.1.

### 3.5 Safety Assessment

Safety data will be summarized by actual treatment received (and in total for selected analyses) based on the Safety Population. Any abnormal laboratory test results or other safety assessments will be reported as AE and listed.

#### 3.5.1 Adverse Events (AEs)

An overview of AEs will be provided including counts and percentages of subjects with the following:

- Any TEAEs (overall and by maximum severity)
- Any study drug related TEAEs
- Any serious TEAEs (SAEs)
- Any TEAEs leading to dose interruption
- Any TEAEs leading to dose reduction
- Any TEAEs leading to discontinuation of study drug
- Any AEs leading to death

Counts and percentages of subjects will also be presented by system organ class and preferred term for TEAEs, SAEs, study drug related TEAEs, and TEAEs leading to discontinuation of study drug.

Listings will be presented for all TEAEs, SAEs, and study drug related TEAEs.

### 3.5.2 Clinical Laboratory Tests

Values and changes from baseline will be summarized using descriptive statistics for each treatment group by visit for protocol-required laboratory tests in Appendix A. All lab results will be listed.

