1.1. Synopsis

Protocol Title:

A 12-weeks, multicentre, randomized, double-blind, placebo-controlled, exploratory, pilot study to evaluate the safety and efficacy of safinamide 200 mg once daily, as add-on therapy, in patients with possible or probable parkinsonian variant of multiple system atrophy.

Short Title:

Safinamide for Multiple System Atrophy

Rationale:

To establish the safety and tolerability of 200 mg of safinamide and to explore whether this dose may offer benefits to patients with the parkinsonian variant of MSA.

Objectives and Endpoints

Objectives	Endpoints
Safety	
To evaluate the safety and tolerability of safinamide, 200 mg od, compared with placebo	 The nature, frequency, severity, relationship (to study drug), actions taken, and outcome of TEAEs and SAEs. Changes in physical and neurological examination findings. Changes in vital sign (heart rate, systolic and diastolic blood pressure) values, including occurrence of abnormalities. Changes in 12-lead ECG parameter measures, including occurrence of abnormalities. Changes in clinical chemistry and hematology values, including shifts from Baseline and occurrence of abnormalities. Number of withdrawals (and reason if given).

Efficacy	
To evaluate the potential efficacy of safinamide 200 mg od, as add-on therapy, on motor function and/or quality of life	 The change from baseline to week 12 in the goniometric measurement for "lateral" and "anterior" displacement Change from baseline at week 12 in Unified MSA Rating Scale, MSA Health-Related Quality of Life (MSA-QoL) scale, Montreal Cognitive Assessment (MoCA) scale, Unified Dystonia Rating Scale (UDRS).

Overall Design:

The study is a randomized placebo controlled double blind study, with two parallel arms, in which participants will be assigned in a 2:1 ratio to receive either safinamide or placebo. Study population is patients diagnosed, less than two years ago, with possible or probable parkinsonian variant of Multiple System Atrophy who are on a stable treatment of levodopa and/or dopamine agonist, anticholinergic and/or amantadine.

Outcome will be assessed after 12 weeks of treatment, when progression is unlikely to be a confounder of change. No Independent Data Monitoring Committee is foreseen.

[figure not shown]
Number of Participants:

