9.4.1.5. Safety Laboratory Parameters

Descriptive statistics for each clinical laboratory test will be presented by study intervention group at each visit. Change from baseline to week 12 values will also be summarized.

According to laboratory normal ranges, laboratory test results will be categorized as low (< lower normal limit), normal (within normal range), and high (> upper normal limit). Shift tables

comparing the distributions of these three categories at baseline versus week 12 will be presented by treatment group for key safety laboratory evaluations.

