10.1.4. Committees Structure

The study protocol is written by a coordinating author with input from various experts. Final draft, after review and input from the CRO, in particular the statistical sections, is reviewed by Sponsor Quality Assurance and Pharmacovigilance units, and approved by the Global Clinical Development Head and the Global Head of Open R&D. The study will be carried out by a CRO, and clinical laboratory tests will be done locally.

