10.2. Appendix 2: Clinical Laboratory Tests

- The tests detailed in Table 1 will be performed by the local laboratory.
- If the local laboratory results are used to make either a study intervention decision or response evaluation, the results must be entered into the CRF.]
- Protocol-specific requirements for inclusion or exclusion of participants are detailed in Section 5 of the protocol.
- Additional tests may be performed at any time during the study as determined necessary by the investigator or required by local regulations.

Table 1: Protocol-Required Safety Laboratory Assessments

Laboratory Assessments	Parameters					
Hematology	Platelet Count				White	
	Red blood cell (Count	RBC)				C) count with rential: rophils
	Hemoglobin					ohocytes
	Hematocrit			Monocytes Eosinophils Basophils		ocytes nophils
Clinical Chemistry ¹	Blood urea nitrogen (BUN)	Potassium		Aspartate Aminotransferase (AST)/ Serum Glutamic- Oxaloacetic Transaminase (SGOT)		Total and direct bilirubin
	Creatinine	Sodium		Alanine Aminotransferase (ALT)/ Serum Glutamic- Pyruvic Transaminase (SGPT)		Total Protein
		Calcium		Alkaline phosphatase		

NOTES:

¹ All events of ALT \geq 3 × upper limit of normal (ULN) and bilirubin \geq 2 × ULN (>35% direct bilirubin) or ALT \geq 3 × ULN and international normalized ratio (INR) >1.5, if INR measured

which may indicate severe liver injury (possible Hy's Law), must be reported as an SAE (excluding studies of hepatic impairment or cirrhosis).

Investigators must document their review of each laboratory safety report.

10.3. Appendix 3: Adverse Events: Definitions and Procedures for Recording, Evaluating, Follow-up, and Reporting

Definition of AE

AE Definition

- An AE is any untoward medical occurrence in a patient or clinical study participant, temporally associated with the use of study intervention, whether or not considered related to the study intervention.
- NOTE: An AE can therefore be any unfavorable and unintended sign (including an abnormal laboratory finding), symptom, or disease (new or exacerbated) temporally associated with the use of study intervention.

Events Meeting the AE Definition

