#### 3.1.4 Summary Statistics

Categorical data will be summarized with counts and percentages of subjects. Continuous data will generally be summarized with descriptive statistics including n (number of non-missing values), mean, median, standard deviation, minimum, and maximum.

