# 5 CHANGES FROM PROTOCOL-SPECIFIED STATISTICAL ANALYSES

The "Enrolled Population" is redefined as "Screened Population"; the "Evaluable Population" is redefined as "Intent-to-Treat (ITT)" Population".

The analyses of efficacy endpoints other than MoCA will be conducted using MMRM instead of ANCOVA.

Shift tables will not be provided for safety assessments since any abnormal findings will be captured in AEs.

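### Local laboratory results get no summary table against the normal range: the SAP keeps pooled values and changes and drops the protocol's shift tables

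*SAP*

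**What the plan says.** The protocol synopsis describes "A 12-weeks, multicentre, randomized, double-blind, placebo-controlled, exploratory, pilot study". Protocol Appendix 2 states: "The tests detailed in Table 1 will be performed by the local laboratory". Protocol 10.1.4 repeats that "clinical laboratory tests will be done locally". No central laboratory is described, and the number of sites is not given.

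Under the safety objective, Protocol section 3 names changes in chemistry and haematology as an endpoint and says that this covers shifts from baseline and the occurrence of abnormal values. Protocol 9.4.1.5 carries that through. It plans descriptive statistics and change to Week 12, and adds: "According to laboratory normal ranges, laboratory test results will be categorized as low", normal or high, with baseline-to-Week-12 shift tables for key tests.

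SAP v2.0 section 3.5.2 plans: "Values and changes from baseline will be summarized using descriptive statistics for each treatment group by visit for protocol-required laboratory tests", plus a listing of all results. SAP 3.1.4 defines the statistics: "Continuous data will generally be summarized with descriptive statistics including n (number of non-missing values), mean, median, standard deviation, minimum, and maximum". SAP section 5 then says: "Shift tables will not be provided for safety assessments since any abnormal findings will be captured in AEs". SAP 2.3.2 shortens the endpoint to the laboratory values themselves.

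**The concern.** Each site's laboratory has its own assay and its own limits, so a pooled mean or range cannot be read against any single upper limit of normal (ULN). The protocol dealt with this by classifying each result against the limits of the laboratory that produced it. Without that classification, no planned laboratory table says how many participants in each arm were, or became, out of range. SAP 3.5.4 and 3.5.5 still count ECG interpretations and examination results; laboratory tests get no such count.

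Laboratory safety belongs to the primary objective, and the endpoint as the protocol words it needs that count. The SAP's reason for dropping the table is that the adverse event data will show abnormalities. If that reason fails, part of the endpoint has no summary.

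**Working it through.** The plan gives no figure on this point, so there is none to reproduce. Steps 1 and 2 compare the documents. Steps 3 to 5 are illustrations, because the documents give no local limits, no SDs and no site count.

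**1. Laboratory outputs planned**

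| Output | Protocol 9.4.1.5 | SAP v2.0 |
|---|---|---|
| Descriptive statistics of values | yes | yes (3.5.2) |
| Change from baseline | yes | yes (3.5.2) |
| Low/normal/high by laboratory range | yes | not mentioned |
| Shift table, baseline to Week 12, key tests | yes | removed (section 5) |
| Listing of all results | not mentioned there | yes (3.5.2) |

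Both rows that place a result against the normal limit are gone, and nothing replaces them.

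**2. Do adverse events replace the table?** SAP 3.5 says that any abnormal laboratory result will become an adverse event. Protocol Appendix 3 makes a laboratory result an adverse event only when the investigator judges it clinically significant. It also excludes abnormalities tied to the underlying disease unless they are worse than expected. Sites record events under the protocol. A result above the local limit that is judged not significant therefore enters no adverse event table. In SAP 3.5.2 it contributes only a number to a mean, and can be found individually only in the listing.

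**3. What a pooled mean can miss.** Treated participants: 48 × 2/3 = 32. Assume a ULN of 45 U/L, that k of the 32 move from 0.6 to 1.5 × ULN, and that the rest do not change. Mean change = k × (1.5 − 0.6) × 45 / 32.
- k = 1: 0.9 × 45 / 32 = 1.27 U/L; shift table 1/32 = 3.1%
- k = 2: 2 × 0.9 × 45 / 32 = 2.53 U/L; shift table 2/32 = 6.25%
- k = 3: 3 × 0.9 × 45 / 32 = 3.80 U/L; shift table 3/32 = 9.4%

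The SAP also reports the maximum, which could show 1.5 × 45 = 67.5 U/L. It would not show how many participants crossed their limit.

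**4. One value, two limits.** Assume local ALT limits of 35 to 55 U/L. A value of 50 U/L is 50/35 = 1.43 × ULN at one laboratory and 50/55 = 0.91 × ULN, within range, at another.

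**5. Effect on spread and on the arm comparison.** Assumptions: mean ULN 45 U/L; baseline 0.55 × ULN with CV 35%; SD of change 0.15 × ULN; 12 sites; each participant tested at one laboratory throughout; 32 versus 16 participants; no treatment effect. Let c be the between-laboratory CV of the ULN. Approximate formulas:
- SD of values = 0.55 × 45 × √[(1 + 0.35²)(1 + c²) − 1]
- SD of change = 0.15 × 45 × √(1 + c²)

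| c | SD of values: formula / simulated | SD of change: formula / simulated | SE of arm difference, simulated: values / change | Mean arm difference in values |
|---|---|---|---|---|
| 0 | 8.66 / 8.57 | 6.75 / 6.70 | 2.66 / 2.08 | 0.01 |
| 0.2 | 10.13 / 9.93 | 6.88 / 6.82 | 3.09 / 2.06 | 0.00 |
| 0.3 | 11.70 / 11.24 | 7.05 / 6.96 | 3.51 / 2.15 | 0.00 |

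All table entries except c are in U/L. From c = 0 to c = 0.3 the simulated SD of values rises by 11.24/8.57 − 1 = 31%, and the SD of change by 6.96/6.70 − 1 = 4%. The mean arm difference stays at about zero.

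**The case against.** Four arguments against the point have weight.

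- **Pooled statistics are not an SAP invention.** Protocol 9.4.1.5 planned them too. This stands: the fault is the loss of the companion range-based table, not the pooling.
- **Change from baseline removes most laboratory differences.** If Screening and Week 12 samples go to the same laboratory, additive offsets cancel, and step 5 shows little effect from scale differences. This largely stands. The documents do not guarantee one laboratory per participant: Protocol section 8 lets routine pre-consent tests serve for screening or baseline, and allows Visit 6 to be held remotely.
- **Serious cases are still caught.** The Appendix 2 liver rule makes the ALT-with-bilirubin (or INR) combination reportable as an SAE, clinically significant results become adverse events, and every result is listed. This stands. What is missing is a count by arm of the less extreme abnormalities.
- **Scaling to local limits has its own cost.** For analytes such as sodium or haemoglobin it replaces familiar units with an index, and it adds noise where limits differ by convention rather than assay. This stands and narrows the fix.

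A reader might go further and infer that the SAP averages unconverted values, that pooling biases the comparison with placebo, or that a drug-related liver signal would be lost. The documents do not support these readings. SAP 3.5.2 does not discuss units, and conversion could sit in the separate programming specifications (SAP section 6). Randomisation keeps the comparison unbiased on average, leaving only chance imbalance in laboratory mix. The Appendix 2 rule works patient by patient, whatever is tabulated.

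**Conclusion.** The point holds as a reporting gap of modest size. Followed as written, SAP v2.0 produces no table of laboratory results against the local normal limit, although the protocol's endpoint includes shifts and abnormalities. The reason given for dropping the shift tables conflicts with the protocol's definition of an adverse event. This conclusion rests on the text alone.

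The cost falls mainly on interpretability and on the spread of values. In the illustration, two treated participants becoming high appear as a 2.53 U/L mean change instead of 2/32. A 30% between-laboratory CV widens the SD of values by 31% but the SD of change by only 4%, with no bias on average. These sizes depend on assumed limits, variability and 12 sites; the comparison for changes also assumes the same laboratory at both visits.

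**What to change.** Amend the SAP before database lock; if that has passed, record the additions as SAP deviations in the study report.

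1. In SAP 3.5.2, add summaries of ALT, AST, alkaline phosphatase and bilirubin, values and changes, as multiples of the ULN of the laboratory that ran the test.
2. Restore the baseline-to-Week-12 low/normal/high shift table by local range from Protocol 9.4.1.5, by arm, and delete the contrary sentence in SAP section 5.
3. State that the other analytes are converted to common clinical units, and do not scale them to local ranges.
4. Reconcile SAP 3.5 and section 5 with protocol Appendix 3 on when an abnormal result is an adverse event.

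The cost is one derived variable and a few tables, with no new samples. Sites already need local limits for exclusion criterion 20 and the Appendix 2 liver rule, and the protocol's categories presuppose them. The documents do not say that the limits are in the study database; if they are not, each laboratory's reference ranges would have to be collected.
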